Preemptive Local Analgesia
with Liposomal Bupivacaine in
Vaginal Hysterectomy: A
Randomized Controlled Study

NCT03907033

September 27, 2019

Preemptive local analgesia with liposomal bupivacaine in vaginal hysterectomy: A randomized, blinded, controlled study

[name]

Principal Investigator

April 25, 2018

REVISED: November 27, 2018

May 2, 2019

September 27, 2019

[name], DO

[name]

[name]

Gynecology

[name]

[name]

Anesthesiology

INTRODUCTION

Reduction in immediate postsurgical pain is important as it results in less opioid requirements and fewer opioid-related adverse events such as central nervous system and respiratory depression, nausea, vomiting, ileus, and pruritus. Decreased postoperative pain may also result in shorter recovery room and hospital stays, and higher patient satisfaction.

Preemptive analgesia in form of uterosacral ligament injection has been shown to be effective for patients undergoing vaginal hysterectomy. Injection of bupivacaine into the uterosacral ligaments has been associated with significantly reduced pain scores in the first three hours after surgery as well as lower total narcotic use within the first 24 hours following surgery (1). Preemptive analgesia with bupivacaine during vaginal hysterectomy is standard practice at our institution as part of a multi-modal pain management platform.

Liposomal bupivacaine is a novel formation of local bupivacaine designed to provide prolonged postsurgical analgesia. The drug is encapsulated in multivesicular liposomes, thereby allowing prolonged drug release for up to 72 hours. Its safety and side effect profile is similar to bupivacaine HCl and normal saline (2). In 2011, the FDA approved of its use for single-dose local administration into surgical sites.

The efficacy of liposomal bupivacaine has been demonstrated in orthopedic procedures, hernia repairs, hemorrhoidectomy, and breast augmentation. When compared to bupivacaine HCl, studies suggest liposomal bupivacaine may be more efficacious in terms of lower pain scores, longer time to first rescue opioid dose, decreased total opioid consumption postoperatively, and shorter length of hospital stays (3).

There are few studies evaluating liposomal bupivacaine in gynecologic surgery. Hutchins et al demonstrated that patients who received transversus abdominis plane (TAP) blocks with liposomal bupivacaine required 50% less total opioid during the first 72 hours following robotic assisted hysterectomy than patients who received bupivacaine (4). While liposomal bupivacaine is promising for management of postoperative pain, it has not yet been studied in vaginal surgery.

The aim of this study is to compare the effects of preemptive analgesia using liposomal bupivacaine mixed with bupivacaine HCl, versus bupivacaine HCl alone for uterosacral ligament injection in patients undergoing vaginal hysterectomy. We hypothesize that the group receiving a combination of liposomal bupivacaine and bupivacaine HCl will report superior postoperative pain management. Enhancement in pain control should confer a decrease in opioid and other analgesic medication requirements, which may contribute to decreased nausea, vomiting, and higher overall patient satisfaction with pain control.

OBJECTIVES

The primary aim of this study is to compare total post-surgical analgesic medication use in the first 72 hours following surgery completion (all opioids in IV morphine equivalents and total mg use of ibuprofen and/or acetaminophen combined).

Secondary outcome measures include mean PACU VAS (0-10) pain score, VAS pain score at 24, 48, and 72 hours post-surgery completion, nausea and emesis at 24, 48, and 72 hours post-surgery completion, urinary retention, and patient satisfaction with pain management at 72 hours and 7-10 days post op.

DESIGN

This is a prospective randomized, blinded, controlled clinical trial.

STUDY MEDICATION

Liposomal bupivacaine is being used per FDA indication (postsurgical analgesia) at an approved dose and route of administration (surgical site infiltration). It is also being given within the FDA labeled doses of the bupivacaine HCl given concomitantly, which recommends mg dose of bupivacaine HCl to liposomal not to exceed 1:2. Safety and efficacy of concomitant use has been prospectively studied (5). This study does not intend to pursue change to labeling or advertising. This study will be carried out in accordance with the applicable United States government regulations and Mayo Clinic research policies and procedures.

PARTICIPANTS

We plan to enroll women 18-85 years old who will be undergoing outpatient vaginal hysterectomy with or without concurrent prolapse repair surgeries at the Mayo Clinic Hospital in Arizona. Participants will be recruited during the preoperative visit and consented with a written form.

Exclusion criteria will include:

- Known history of hepatic disease evidenced by AST or ALT greater than normal values
- Known history of renal disease evidenced by serum Cr greater than normal values
- Known history of prolonged QT ($QT_c >$ than 500 m/s)
- Opiate tolerance noted by daily use of greater than 20 mg morphine daily oral equivalents per day for minimum one month prior to surgery
- Allergy or contraindication to amide local anesthetics, celecoxib, ketorolac, NSAIDS, acetaminophen, gabapentin, sulfa drugs, or ondansetron. Patients allergic to both oxycodone and hydromorphone

- Patients with acute GI bleed in < 6 months of study
- Adults lacking capacity to consent

MATERIALS AND METHODS

Randomization and Blinding:

Redcap software will generate a randomization list in one-to-one ratio to assign patients to either the study group (receiving both liposomal bupivacaine and bupivacaine HCl) or control group (receiving bupivacaine only). All subjects will be recruited and assigned according to their priority at admission. The pharmacist will use this randomization list and dispense the medication sequentially. Patients, care team in recovery, study team members collecting and recording data, and statisticians will be blinded to randomization assignment. The surgical team and pharmacy will be un-blinded. All patients will be documented in EMR as receiving liposomal bupivacaine to ensure the blind is maintained and to ensure that safety features in the EMR for all patients receiving liposomal bupivacaine are activated.

TREATMENT GROUPS

Patients in both groups will be given a total volume of 40ml and dose of 100 mg plain bupivacaine:

- Patients in the study group will receive a mixture of 0.5% bupivacaine HCl and liposomal bupivacaine in 1:1 ratio. 10cc of the mixture will be injected bilaterally into each uterosacral ligament prior to the colpotomy incision. After entry into the posterior cul-de-sac, an additional 10cc will be injected bilaterally into the deeper uterosacral ligaments (diagram attached as appendix 3).
- Patients in the control group will receive 0.25% bupivacaine HCl. 10cc will be injected bilaterally into each uterosacral ligament prior to the colpotomy incision. After entry into the posterior cul-de-sac, an additional 10cc will be injected bilaterally into the deeper uterosacral ligaments.

We plan to standardize preoperative medication, intraoperative anesthetic regimen, medication, administration in the recovery area, and discharge medication treatment (see appendix 1). Care will include key elements of a validated enhanced recovery protocol (6).

DATA COLLECTION

Demographic data including age, BMI, medical and surgical history, indication for surgery, and degree and type of pelvic organ prolapse will be collected.

Intraoperative fentanyl use will be recorded from the anesthesia record. Immediate postoperative opioid use will be retrieved from the EMR until discharge from PACU. Immediate nausea and emesis will be determined by total dose of antiemetics in PACU. Urinary retention will be determined as post void residual greater than 200 ml on catheterization or bladder scan. Patients will be offered PO opioid analgesics as first line therapy in PACU. Number and percentage of patients receiving intravenous opioids as second line therapy, thus failing PO as first line therapy in PACU will be recorded; however they will remain in the study.

Other intraoperative and immediate postoperative data will include completed procedure, surgery time, estimated blood loss, final pathology, and presence of failed voiding trial, length of stay in recovery, and numbers and reason for any unplanned admissions. Unplanned admission patients' data will be excluded and be recorded as a treatment failure.

All patients will be discharged home with a diary to record analgesic use, VAS pain scores, and presence of nausea and emesis through 72 hours post-surgery (POD 3). Opioid use will be documented as total tablets of 5 mg oxycodone, hydromorphone 2mg, and non-opioid medication use as total tablets of acetaminophen 500 mg and/or ibuprofen 600 mg. VAS (0-10) pain scores will be logged at 6 hour intervals. Nausea and emesis will be documented as how many times patients felt nauseated, how many times they vomited, and total tablets of anti-emetic. Patients will be emailed twice a day with a link to record their documented scores. Those who prefer not to complete the surveys electronically will have the option to complete the paper questionnaire and diary. Those choosing the paper option will receive a daily phone call from study personnel blinded to study groups to remind them to complete their diary and questionnaire. Patient satisfaction for pain control will be assessed as a 0-10 scale question at the 72 hour mark and again at 7 to 10 days postop via telephone.

Allergic reaction to liposomal bupivacaine and local anesthesia toxicity will be assessed immediately on presentation to PACU, prior to discharge, and assessed by telephone and documented up to the 7 to 10th post-operative day. All doses of liposomal bupivacaine are within manufacturer labeling, and this is an FDA “on label” use of the drug (surgical site tissue infiltration). Concomitant bupivacaine HCl with liposomal bupivacaine doses are within manufacturer “on label” recommended ratio of 1:2. Intralipid 20% for local anesthetic toxicity treatment will be immediately available at all times prior to discharge. All data will be entered into HIPAA-compliant REDCap software.

SAMPLE SIZE

We plan to enroll and randomize 104 patients with the goal of obtaining complete data on at least 96 (47 per group) assuming a 10% loss to follow up. With a sample of 96, we achieve 80% power to detect a 30% difference in total opioid use at the 72 hour mark corresponding to an effect size of 0.6 at an alpha 0.05.

DATA ANALYSIS

Statistical summary descriptives such as mean, median, standard deviation, first quartile, third quartile and range for quantitative data, and frequency and proportions for categorical data will be provided. The objectives of the study comprise the group comparisons between combination liposomal bupivacaine/bupivacaine HCl vs. bupivacaine HCl only for total opioid use in morphine equivalents, total non-opioid use, VAS pain scores, episodes of emesis, total antiemetic use, and patient satisfaction. The normality assumptions will be checked and the appropriate parametric tests such as the two independent sample t-test or non-parametric tests such as the Wilcoxon rank sum test will be used. Group associations with categorical variables will be tested using the Chi-square or Fishers' exact test. The significance level is at 0.05.

SAFETY MONITORING

All patients will be continuously monitored for local anesthetic toxicity or other reaction to liposomal bupivacaine for the entire surgical scope of care. During surgery standard ASA monitors will be in place and in recovery vital signs every 15 minutes with continuous telemetry and pulse ox, with a minimum 2:1 RN monitoring. They will remain in recovery a minimum of 4 hours post op. Continuous surveillance for medication reaction or local anesthetic toxicity including but not limited to tinnitus, perioral numbness, mental status changes, cardiac arrhythmia, respiratory compromise, rash, or hives. 20% intralipid for treatment of toxicity will be available at all times. Patients will also be discharged with specific education regarding signs and symptoms for local anesthetic toxicity and instructions to call the on call physician with mild symptoms and present to the ED if moderate or severe symptoms.

ADVERSE EVENTS

The investigator/study team will report to the Mayo IRB any UPIRTSOs and NonUPIRTSOs according to the Mayo IRB Policy and Procedures.

An adverse event is defined as an untoward or undesirable experience associated with the use of a medical product (i.e. drug, device, biologic) in a patient or research subject. All adverse events that are considered related to the direct use of liposomal bupivacaine will be defined, collected, and reported.

The principal investigator will be responsible for determining whether an event is related to the direct use of liposomal bupivacaine. An AE will be considered unexpected if the nature, severity, or frequency of the event is not consistent with the risk information previously described for the standard of care procedure or in the package insert for liposomal bupivacaine.

All study-related AEs will be followed until stabilization or resolution.

ADVERSE EVENT REPORTING PERIOD

For this study, the study treatment follow-up period is defined as 7-10 days after the procedure when they are contacted by the study team.

MEDICAL MONITORING

It is the responsibility of the Principal Investigator to oversee the safety of the study at his/her site. This safety monitoring will include careful assessment and appropriate reporting of adverse events as noted above, as well as the construction and implementation of a site data and safety-monitoring plan. Medical monitoring will include a regular assessment of the number and type of serious adverse events.

FUNDING

Pacira Pharmaceuticals, Inc. is funding the study. Pacira Pharmaceuticals, Inc. will pay the institution to cover costs related to running the study; however, they will have no role in randomization, patient care, assessment of data, or development of conclusions. Attempts will be made to publish the results independent of outcome, even for a negative study.

REFERENCES

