- b. Control group: (OR nurse to retrieve, surgeon to inject)
 - i. Inject 10cc of 0.25% bupivacaine into each uterosacral ligament prior to colpotomy
 - ii. After entry into posterior cul-de-sac, inject additional 10cc of 0.25% bupivacaine into deeper uterosacral ligaments bilaterally
 - iii. Total injection = 40ml
- c. Anesthesia:
 - i. All patients will receive general endotracheal anesthesia
 - ii. Induction with Fentanyl 1-2 mcg/kg, Propofol/lidocaine, succinylcholine/rocuronium
 - iii. Maintenance with Sevoflurane in air oxygen mixture, and fentanyl prn to a case maximum of 400 mcg, no additional opioids
 - iv. Background propofol infusion (25-75 mcg/kg/min)
 - v. No ketamine
 - vi. Prophylactic antibiotic prior to incision
 - vii. Reversal at provider's discretion with glycopyrrolate/neostigmine, or sugammadex
 - viii. Ketorolac 15mg IV during wound closure
 - ix. Ondansetron 4mg IV during wound closure

III. Recovery:

- a. PACU
 - i. First line: IV Tylenol, PO Oxycodone 5-10 mg or PO hydromorphone 2 - 4 mg mild (VAS 0-4), moderate (5-6), or severe (7-10) pain (Gyn service order)
 - ii. Second line: Fentanyl 25 mcg q 5 min prn to max of 200 mcg for severe pain (7-10) (Gyn service order)
 - iii. Third line: hydromorphone 0.2 mg IV q 5 min to max of 2 mg for severe pain (7-10) refractory to fentanyl (Gyn service order)
 - iv. Ondansetron 4 mg IV PRN up to 2 doses (Gyn service order)
 - v. Promethazine 6.25 mg IV PRN one dose for refractory nausea up to 2 doses (Gyn service order)
 - vi. May give other anti-emetics as needed.
- b. Discharge Medications
 - i. Acetaminophen 1000 (2 OTC 500 mg strength) mg Q8 hrs PRN mild (0-4) to moderate (5-6) pain

- ii. Ibuprofen 600 (prescription 600 mg strength) mg Q8 hours PRN mild (0-4) to moderate (5-6) pain
- iii. Oxycodone 5 or 10 mg Q4 hrs PRN for moderate (5-6) to severe (7-10) pain. Patients will be discharged with two prescriptions: the first to be filled for 10 tablets, the second for additional 20 tablets if needed.
- iv. Hydromorphone 2 or 4 mg Q4 hrs PRN for moderate (5-6) to severe (7-10) pain. Patients will be discharged with two prescriptions: the first to be filled for 10 tablets, the second for additional 20 tablets if needed.
- v. Ondansetron 4 mg PO Q6 hours PRN for nausea
- vi. Prochlorperazine 10 mg PO Q8 hours PRN for nausea

APPENDIX 2

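### The primary aim contains two quantities, opioid use and a pooled non-opioid mg total, and the plan never says which one decides the trial

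*Combined protocol and SAP*

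**What the plan says.** - **Objectives.** There is one primary aim, total analgesic use from surgery completion to 72 hours, measured as "all opioids in IV morphine equivalents and total mg use of ibuprofen and/or acetaminophen combined". The secondary list that follows covers pain, nausea and emesis, urinary retention and satisfaction. Non-opioid use is not in it, so it stands in the primary aim.
- **Introduction.** The gynecologic precedent is an opioid result: patients given the liposomal product "required 50% less total opioid during the first 72 hours following robotic assisted hysterectomy". The hypothesis covers both parts: "Enhancement in pain control should confer a decrease in opioid and other analgesic medication requirements".
- **Sample Size.** The only calculation claims "80% power to detect a 30% difference in total opioid use at the 72 hour mark", with effect size 0.6 and alpha 0.05.
- **Data Analysis.** The comparisons form one unranked list that includes "total opioid use in morphine equivalents, total non-opioid use, VAS pain scores". For quantitative outcomes, depending on a normality check, "the two independent sample t-test or non-parametric tests such as the Wilcoxon rank sum test will be used". On error control the section says only "The significance level is at 0.05".
- **Appendix I, Data Collection.** Part IV (PACU) lists opioids as the only analgesic total. Part V (to 72 hours) lists opioids in IV morphine equivalents and non-opioids as tablet counts, as separate items.

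**The concern.** A confirmatory trial needs one stated rule that turns its results into a conclusion. Here the primary aim has two parts with no common scale. The analysis tests each part at the full 0.05, and nothing says whether opioid use alone, either part or both parts must be significant. The deciding result could therefore be chosen after the data are seen.

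Disagreement between the two is plausible. In the discharge medications, opioids and non-opioids are all taken as needed and overlap at moderate pain; the oxycodone entry reads "Oxycodone 5 or 10 mg Q4 hrs PRN for moderate (5-6) to severe (7-10) pain", and acetaminophen and ibuprofen are listed for mild to moderate pain. A patient may replace one with the other, so one total can fall while the other stays level or rises.

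Two smaller points concern the non-opioid part only. A raw mg sum gives one listed acetaminophen dose (1000 mg) more weight than one listed ibuprofen dose (600 mg). Also, the 72-hour window opens at surgery completion and IV acetaminophen is among the first-line PACU drugs, yet the PACU data list has no item for it.

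**Working it through.** **Inputs from the plan.** Effect size d = 0.6 for opioid use, alpha 0.05, 1:1 allocation, 47 per group. Sidedness is not stated; two-sided is assumed. (The plan also gives 96 in total, while 2 × 47 = 94; at 48 per group power is less than one percentage point higher.)

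**Assumed, because the plan gives no figures.** Non-opioid effect d2 = 0.6 or 0.4; correlation r between the two totals from -0.5 to 0.9.

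**1. The plan's own figure.** The two-sample t-test needs 44.6 per group for 80% power at d = 0.6. Under normal data the Wilcoxon test needs π/3 times as many: 44.6 × 1.047 = 46.7, so 47 per group. Power at 47 per group is 82.1% (t-test) and 80.3% (Wilcoxon). The stated sample size therefore reproduces for opioid use alone.

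**2. If either result may count.** Family-wise error is 1 − P(|Z1| < 1.96 and |Z2| < 1.96), with Z1 and Z2 bivariate normal with correlation r. At r = 0 this is 1 − 0.95² = 0.0975. At r = ±0.5 it is 0.0907, and at r = ±0.9 it is 0.0704.

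**3. If both must be significant, and how often exactly one is.** Simulated t-tests, 47 per group; joint power counts both results in the favourable direction.

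| r | Both, d2 = 0.6 | Exactly one, d2 = 0.6 | Both, d2 = 0.4 | Exactly one, d2 = 0.4 |
|---|---|---|---|---|
| -0.5 | 0.647 | 0.346 | 0.346 | 0.612 |
| 0 | 0.674 | 0.294 | 0.398 | 0.510 |
| 0.5 | 0.716 | 0.210 | 0.448 | 0.408 |
| 0.9 | 0.774 | 0.094 | 0.483 | 0.339 |

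The r = 0, d2 = 0.6 entry agrees with direct arithmetic: 0.821² = 0.674. The columns for exactly one significant result need no decision rule; they show how often the plan as written would reach a split result under these assumptions.

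**4. Cost of keeping both parts primary.**
- Alpha split, 0.025 each: opioid power by t-test falls to 73.5% at 47 per group. 80% needs 55 completers per group, that is 110 / 0.9 = 122.2, so 123 randomised.
- Both required, r = 0, d2 = 0.6: 59 completers per group give 0.807, that is 118 / 0.9 = 131.1, so 132 randomised.
- On the Wilcoxon basis that reproduces the plan's 47, these become 57 and 61 completers per group.

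**The case against.** The best counter-argument is that opioid use is already the implied primary outcome. It is the only quantity with a power calculation, it uses the same 72-hour window as the aim, it comes first in the analysis list, and the cited gynecologic precedent is an opioid result. On that reading one sentence is missing and the sample size is sound. This stands as the likely intent and is why the fix below follows it. It does not settle the matter: Sample Size never calls opioid use primary, and the Objectives give non-opioid use the same standing.

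The word combined in the primary aim could also mean a single composite of all analgesics. That would need a common scale, which the plan does not give, and Data Analysis lists the parts separately. On that reading the primary outcome could not be computed as written, so a correction is still needed.

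On error rates, the 7.0% to 9.75% counts false positives in both directions. The chance of at least one false result favouring the study arm is about 3.5% to 5.0% over the same correlations (4.9% at r = 0). That is a fair qualification, but the nominal one-direction rate is 2.5%, so at r = 0 it still roughly doubles.

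Finally, the disagreement rates and joint power rest on assumed non-opioid effects and correlations. They illustrate what is at stake and do not estimate this trial's risk. One significant and one non-significant result is also weaker than two results in opposite directions.

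**Conclusion.** The concern holds and must be fixed. Followed as written, the plan has two primary comparisons, no rule linking them, no error control across them, and a stated power that covers only one. How much this costs depends on which rule the authors intended: error inflation if either result suffices, a power shortfall if both are required, and only missing wording if opioid use alone decides. The opioid power and the family-wise error rest on the plan's inputs, two-sided testing and, for the error rate, the correlation range; the joint power and split-result figures also rest on the assumed non-opioid effects.

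The mg-sum weighting and the PACU gap are minor. No between-arm bias is shown, the size of the PACU gap is unknown, and neither touches the opioid total.

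**What to change.** Before unblinding, amend Objectives and Data Analysis as follows.

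1. Name total opioid use, in IV morphine equivalents from surgery completion to 72 hours, as the single primary outcome at two-sided 0.05.
2. Make non-opioid use secondary. Report acetaminophen and ibuprofen totals separately, with confidence intervals, beside the primary result so that substitution is visible. Drop the raw mg sum; the tablet counts already planned give the home part of each total.
3. If a confirmatory non-opioid claim is wanted, test it only after a significant opioid result, in an order fixed before unblinding.
4. Record PACU IV acetaminophen in mg from the EMR and include it in the 72-hour acetaminophen total.

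The cost is wording and one EMR field. The 104 patients and the opioid power are unchanged. The drawback is that the primary test no longer covers the whole stated aim of total analgesic use. Keeping both parts primary is also valid if the rule is written down, but it needs the larger samples shown in the working.

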APPENDIX I

DATA COLLECTION

- I. Demographic data
 - a. Age/date of birth
 - b. BMI
- II. Preoperative data
 - a. Indication for surgery
 - b. Medical history
 - c. Surgical history
- III. Operative data
 - a. Surgery performed
 - b. Operative time
 - c. Pathologic diagnosis
 - d. Total fentanyl dose in mcg during surgery
 - e. Complications during surgery; anesthetic and surgical
- IV. Immediate postoperative data (PACU until discharge)
 - a. Total opioid use in mg morphine IV equivalents
 - b. Antiemetic use as total doses IV antiemetics
 - c. VAS pain scores: cumulative in PACU until discharge
 - d. Urinary retention: determined as post void residual greater than 200 ml on catheterization or bladder scan.

V. Postoperative data to 72 hour (POD 3)

- a. Total opioid use in mg morphine IV equivalents
- b. Non-opioid medication use in total tablets of 600 mg ibuprofen and 500 mg acetaminophen
- c. VAS pain scores: mean of cumulative in PACU until discharge, day of discharge at home, 24 hours (POD 1), 48 hours (POD 2), 72 hours (POD 3). Home VAS scores will be mean of 6 hour intervals each day
- d. Times patients felt nauseated: day of discharge at home, 24 hours (POD 1), 48 hours (POD 2), 72 hours (POD 3).
- e. Episodes of emesis: day of discharge at home, 24 hours (POD 1), 48 hours (POD 2), 72 hours (POD 3).
- f. Antiemetic medication use: day of discharge at home, 24 hours (POD 1), 48 hours (POD 2), 72 hours (POD 3).
- g. Indication for admission (if applicable)
- h. Patient satisfaction with postoperative pain control (0-10; 0=unsatisfied, 10=very satisfied)
 - i. 72 hours
 - ii. 7-10 days post op

ANESTHESIA PROTOCOL

I. Preoperative:

- a. Up to 4 mg Midazolam at providers discretion on transport to OR
- b. Celecoxib 400mg PO (Gyn service order)
 - i. For patients 18-64 years old
- c. Acetaminophen 1000mg PO (Gyn service order)
- d. Decadron 4mg (Gyn service order)
- e. Gabapentin 300-600mg PO (Gyn service order)
 - i. For patients 18-59 years old, order 600mg
 - ii. For patients 60-69 years old, order 300 mg
 - iii. Do not give if >70 years old

II. Intraoperative:

- a. Study group: (OR nurse to retrieve, surgeon to inject)
 - i. Mix 20cc 0.5% bupivacaine HCl and 20 cc liposomal bupivacaine in 1:1 ratio
 - ii. Inject 10cc of mixture into each uterosacral ligament prior to colpotomy
 - iii. After entry into posterior cul-de-sac, inject additional 10cc of mixture into deeper uterosacral ligaments

- iv. Total injection = 40 ml

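### The listed baseline data hold no preoperative pain score or opioid dose, so the pain comparisons forgo a covariate that costs one question; the loss is precision, not validity

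*Combined protocol and SAP*

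**What the plan says.** The DATA COLLECTION section describes the baseline data in one sentence: "Demographic data including age, BMI, medical and surgical history, indication for surgery, and degree and type of pelvic organ prolapse will be collected". Appendix I repeats the topic under "II. Preoperative data" with three entries: the reason for operating and two history items. Neither list has a pain score.

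The first pain entry in Appendix I comes after surgery, under the immediate postoperative data: "VAS pain scores: cumulative in PACU until discharge". OBJECTIVES names the pain outcomes as "mean PACU VAS (0-10) pain score, VAS pain score at 24, 48, and 72 hours post-surgery completion", and states the primary aim as to "compare total post-surgical analgesic medication use in the first 72 hours following surgery completion".

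There is an occasion to ask before surgery. PARTICIPANTS says: "Participants will be recruited during the preoperative visit and consented with a written form". The same section excludes women with "daily use of greater than 20 mg morphine daily oral equivalents" sustained for at least a month. Staff must therefore establish opioid intake to apply the criterion, but the dose is not a listed data item for the women who enter.

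DATA ANALYSIS plans a two-sample t-test or, if normality fails, a Wilcoxon test. It names no covariates.

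**The concern.** Pain is measured repeatedly after surgery on a 0-10 scale, and the protocol's introduction expects better pain control to lower analgesic use. A score on the same scale before surgery is a natural covariate for the VAS outcomes and a possible one for opioid use. The eligibility criteria leave room for it to vary. Women with preoperative pelvic pain are not excluded, and neither are opioid users at or below the threshold.

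This differs from a general request for covariate adjustment. Age, BMI and prolapse stage will be in the dataset, and an adjusted analysis could still be added. A preoperative VAS that was never asked cannot be recovered after the operation. If it is prognostic, the trial gives up precision, and the baseline table cannot show whether the arms were alike on the scale on which pain is compared.

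**Working it through.** **Inputs.** From SAMPLE SIZE: standardised effect 0.6 for 72-hour opioid use, alpha 0.05, 80% power, 47 per group. Two-sided testing is assumed, because the plan does not state sidedness. The correlation r between preoperative pain and an outcome appears nowhere in the documents, so it is an assumption, shown from 0 to 0.5.

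**Step 1: the plan's own figure.** For d = 0.6, a two-sided t-test at 80% power needs 44.6 per arm. Dividing by the Wilcoxon test's asymptotic relative efficiency of 0.955 gives 44.6 / 0.955 = 46.7, or 47 per arm, as stated. At 47 per arm, power is 80.3% with the Wilcoxon allowance and 82.1% for the t-test. The stated design therefore reaches its target without a covariate.

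**Step 2: gain from adjustment.** With a linear covariate the residual SD is SD × √(1 − r²). The standardised effect becomes 0.6 / √(1 − r²), and the equivalent gain in sample size is 1 / (1 − r²) − 1. t-test power at 47 per arm:

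| Assumed r | 1 − r² | Equivalent extra patients | Power, opioid effect 0.6 SD |
|---|---|---|---|
| 0 | 1.00 | 0% | 82.1% |
| 0.1 | 0.99 | 1% | 82.5% |
| 0.2 | 0.96 | 4% | 83.6% |
| 0.3 | 0.91 | 10% | 85.5% |
| 0.4 | 0.84 | 19% | 88.1% |
| 0.5 | 0.75 | 33% | 91.4% |

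For example, at r = 0.3 the gain is 1 / 0.91 − 1 = 9.9%. The approximation ignores the single degree of freedom spent on the covariate.

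The sample-size column applies to any outcome with that r. The power column applies only to opioid use, because 0.6 is the opioid effect size and no effect size or SD is given for VAS. For opioid use the covariate is also a different kind of measurement from the outcome, so its r is the more speculative of the two.

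**Step 3: size of a chance imbalance.** The standard error of a standardised baseline difference with 47 per arm is √(2/47) = 0.206. A difference of 0.2 SD in preoperative pain is thus about one standard error. It would move the unadjusted VAS difference by 0.2 × r: 0.02 SD at r = 0.1, 0.04 at r = 0.2 and 0.10 at r = 0.5. The unadjusted between-arm difference has the same standard error of 0.206 SD, so even the largest of these shifts is about half of it (0.10 / 0.206 = 0.49).

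**The case against.** **No bias.** A reader might infer that, without a baseline score, a treatment effect cannot be told apart from a preoperative pain imbalance. The documents do not support that. Assignment is randomised one-to-one, and the planned tests keep their type I error without adjustment. Chance imbalance in any prognostic variable, measured or not, is already part of the standard error, as step 3 shows. This objection stands in full: the loss is precision and description.

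**Not wholly invisible.** A reader might also infer that an imbalance would leave no trace. The reason for surgery and the medical history are collected and may reveal chronic or pelvic pain. The opioid exclusion removes one extreme. This stands in part: these items are indirect and give no score on the outcome scale.

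**The benefit is assumed.** Nothing in the documents shows that preoperative pain is prognostic here. If many women score near zero before surgery, r could be 0 to 0.1 and the gain 1% or less. This stands, and is why the range starts at zero.

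**Absence is not fully proven.** The DATA COLLECTION sentence is worded as a non-exhaustive list, and only the heading of Appendix 2 is in the available text, so an item there cannot be ruled out. This is a limited doubt, since the itemised preoperative list in Appendix I shows none.

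**The primary test should not be displaced.** Making an adjusted model the main opioid analysis on an unsupported r would go too far. This also stands, and the fix respects it.

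**Conclusion.** The point holds as a cheap, optional improvement. The listed baseline data contain neither a preoperative pain score nor the preoperative opioid dose, and no adjusted analysis is planned. The cost is some precision, and the means to describe and adjust for a chance imbalance on the pain scale.

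Its size depends wholly on the assumed r. The gain is small below about r = 0.3 and becomes material from there. It should not be read as a finding that the trial is underpowered, since the design reproduces its stated 80% without a covariate. Nor can the opioid power figures be quoted for VAS. The calculation rests on two-sided testing, a linear relation and 47 per arm. With 48 per arm the t-test figures run from 82.9% at r = 0 to 91.9% at r = 0.5, so that choice does not alter the conclusion.

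**What to change.** 1. In DATA COLLECTION and in the preoperative part of Appendix I, add one 0-10 VAS pain score, taken at the preoperative visit, and the daily opioid dose that must already be established to apply the exclusion. The exclusion itself is untouched.
2. In DATA ANALYSIS, pre-specify that the PACU, 24, 48 and 72 hour VAS comparisons adjust for preoperative VAS by ANCOVA, or by a rank-based version if normality fails.
3. Keep the planned unadjusted test as the main analysis of 72-hour opioid use. Add the version adjusted for preoperative VAS as a pre-specified supportive analysis.
4. Report preoperative VAS and opioid dose by arm in the baseline table.

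The cost is one extra question and one recorded field at a visit that already takes place, a short addition to the analysis text, and about one degree of freedom per adjusted comparison. The downside is that any patients already enrolled would lack the score; a missing-value indicator in the adjusted model can handle this and keep them in the analysis.
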